The primary outcome is the difference between treatment groups in key proteins measured in neuronally derived exosomes. Based on the previous work of Goetzl et al(30,31) between group differences of 4.9 SD were achieved in these measures. Assuming a difference of half of this magnitude (2.45 sd), a sample size of 4 participants per arm would be needed to give 80% power to detect a difference between groups to the 0.05 level of significance. The additional participants receiving phenserine will provide valuable information for safety reporting.

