10.3.1. General Considerations

The statistical analysis plan for this study is designed to assess the efficacy, safety, and pharmacokinetic properties of phenserine compared to donepezil in participants with early or mild Alzheimer's Disease (AD). Analyses will be conducted on a modified intent-to-treat (mITT) population, which includes all randomized participants who receive at least one dose of study medication and have at least one post-baseline assessment. All statistical tests will be two-sided, with a significance level set at 0.05.

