10.3.6. Exploratory Endpoints Analysis

Exploratory endpoints focus on changes in blood and CSF biomarkers and their relationship with clinical outcomes.

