2.4 Timing of Outcome Assessments

The timing of all outcome assessments is predefined in the study protocol and summarized in the Schedule of Activities (SoA) (Protocol Section 1.3, Table 1). Outcome measures are collected at screening, baseline, and at scheduled on-treatment and follow-up visits during the 8-week treatment period and safety follow-up.

For all clinically planned outcome measures, visits should occur within the predefined visit windows. Assessments performed outside the allowable visit window will be considered protocol deviations, unless otherwise justified and documented. Only assessments obtained within the protocol-specified windows will be used for primary and secondary analyses.

The target days and visit windows relevant for efficacy, pharmacodynamic, pharmacokinetic, and safety analyses are defined as follows:

Visit Label	Visit Window
Screening	Within 28 days prior to baseline
V1: Baseline / Randomization	Day 0
V2: Week 2	Day 14 ± 3 days
V3: Week 4	Day 28 ± 3 days
V4: Week 6	Day 42 ± 3 days
V5: Week 8 / End of Treatment	Day 56 ± 3 days
Safety Follow-up / EOS	Within 28 days after last dose

Assessments collected outside the visit window will not be included in the primary analysis but may be listed and summarized descriptively.

3 Study Design Overview

- Design: Open-label, randomized (6:2), parallel-group Phase 1b study
- Treatment Arms:
 - Phenserine (dose-escalation up to 10 mg TDS)
 - Donepezil (5–10 mg OD)
- Treatment Duration: 8 weeks
- Sample Size: n = 16 (Phen: n=12; Donepezil: n=4)

Given the exploratory nature and small sample size, all analyses will be descriptive, and estimation focused.

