9.1 CSF and Plasma Biomarkers

- Change from baseline at Week 8
- Descriptive summaries only
- Correlation analyses with exosome biomarkers (Spearman)

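### SAP 9.1 plans Spearman correlations of CSF/plasma markers with exosome markers without accounting for arm; if the arms are pooled, two markers that both differ between arms can look correlated with no association within either arm

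*SAP*

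**What the plan says.** SAP section 9.1 has three lines. The CSF and plasma variable is "Change from baseline at Week 8", the presentation is "Descriptive summaries only", and the link to the primary markers is "Correlation analyses with exosome biomarkers (Spearman". It does not say whether the correlation is pooled, done by arm or adjusted for arm. It also does not say whether exosome values enter as changes or levels, or from which of their visits.

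Nothing elsewhere fills the gap. Protocol section 10.3.6 speaks of "changes in blood and CSF biomarkers and their relationship with clinical outcomes", which is a different relationship. Protocol section 3.2.3 compares cognitive results, not CSF or plasma results, with exosome changes. The SAP does handle arm where the exosome markers are the response: section 7.2 has treatment and its interaction with visit as fixed effects.

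Four other statements bear on the point:

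- The SAP's design overview (section 3) gives "Sample Size: n = 16 (Phen: n=12; Donepezil: n=4".
- Protocol section 10.2 hypothesises that the arms differ on the exosome markers and, as an exploratory hypothesis, on the blood and CSF markers.
- Protocol section 9.21 has blood and CSF biomarkers taken at Screening and Week 8 only. Footnote 7 to protocol Table 1 makes the Week 8 CSF sample voluntary.
- SAP sections 2.3.1, 2.3.2 and 5 treat these analyses as exploratory, with p-values reported descriptively and no formal testing.

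**The concern.** Read literally, the line leads a programmer to one rank correlation per marker pair across all participants. Arm is then a common cause of both variables. If phenserine moves an exosome marker and, separately, a CSF or plasma marker relative to donepezil, the two arms form two displaced clouds. The pooled coefficient is then non-zero even if, within each arm, a person's change in one marker says nothing about the change in the other. It restates two arm differences as a link between markers and adds no independent evidence of one.

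This arises when both protocol 10.2 hypotheses are true, which is the result the trial is looking for. Calling the analysis descriptive does not help, because the coefficient itself is what would mislead. Protocol section 2.3.3 says that the exosome, blood/CSF and cognitive results together will be used to select doses and outcome measures for Phase 2. A misread association could therefore carry into that choice.

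**Working it through.** **Inputs.** Arm sizes 12 and 4 (SAP section 3), so the phenserine share is p = 0.75. Planning difference for exosome proteins: 2.45 SD, half of 4.9 SD (protocol sections 10.3 and 10.4). Nominal two-sided level 0.05 (protocol section 10.3.1), used here only as a yardstick. The documents give no expected arm difference for any CSF or plasma marker and no number of Week 8 CSF samples, so both are assumed ranges.

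**1. The plan's own figure.** Protocol section 10.3 states: "Assuming a difference of half of this magnitude (2.45 sd), a sample size of 4 participants per arm would be needed", for 80% power. The noncentral t distribution gives 61.9% power at 3 per arm and 82.1% at 4 per arm, so 4 per arm is reproduced. The documents state no figure for the correlation.

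**2. Size of the induced correlation.** Let each marker have SD 1 within arm, zero within-arm correlation, and arm shifts d1 and d2. With q = p(1−p) = 0.75 × 0.25 = 0.1875, the pooled covariance is q·d1·d2 and the pooled variances are 1 + q·d1² and 1 + q·d2². Hence

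r = q·d1·d2 / √[(1 + q·d1²)(1 + q·d2²)].

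- d1 = d2 = 2.45: q·d² = 0.1875 × 6.0025 = 1.125, so r = 1.125/2.125 = 0.530.
- d1 = 2.45, d2 = 1: r = 0.459/√(2.125 × 1.1875) = 0.289.
- d1 = d2 = 1: r = 0.1875/1.1875 = 0.158.
- Either shift zero: r = 0.

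**3. Spearman at 12 + 4.** Simulation of 100,000 trials per row with normal markers and zero within-arm correlation. The pooled coefficient was judged against a permutation critical value (0.500 for n = 16). The partial coefficient uses arm-centred ranks.

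| Exosome shift (SD) | Other marker's shift (SD) | Pooled: mean rho | Pooled: p<0.05 | Partial: mean rho | Partial: p<0.05 |
|---|---|---|---|---|---|
| 0 | 0 | 0.00 | 5.1% | 0.00 | 5.1% |
| 0.5 | 0.5 | 0.04 | 5.4% | 0.00 | 5.1% |
| 1 | 1 | 0.15 | 8.6% | 0.00 | 5.2% |
| 2.45 | 0 | 0.00 | 5.1% | 0.00 | 5.1% |
| 2.45 | 1 | 0.27 | 16.8% | 0.00 | 5.6% |
| 2.45 | 2.45 | 0.47 | 46.5% | 0.00 | 6.7% |
| 2.45 | −2.45 | −0.47 | 46.5% | 0.00 | 6.7% |

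Arm adjustment removes the bias in the coefficient. At large shifts its nominal rejection rate stays slightly above 5%.

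**4. Fewer CSF pairs.** With 2.45 SD in both markers, 8 + 3 pairs give a mean pooled rho of 0.50 and 33.0% nominal significance; 6 + 2 pairs give 0.48 and 19.6%. The coefficient stays about the same size, and the rejection rate falls because the sample is smaller.

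**5. Precision of the adjusted coefficient.** By the Fisher z approximation with one covariate, the 95% interval around zero is ±tanh[1.96/√(n − 1 − 3)]. That is ±tanh(1.96/√12) = ±0.51 at n = 16, ±tanh(1.96/√7) = ±0.63 at n = 11, and ±tanh(1.96/√4) = ±0.75 at n = 8. The unadjusted interval at n = 16 is ±tanh(1.96/√13) = ±0.50, so the price of adjustment is small and the real limit is the sample.

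**The case against.** The strongest reply is that the SAP does not specify a wrong analysis; it leaves one unspecified, in a section labelled descriptive, in a trial that disclaims formal inference. SAP section 5 already puts the emphasis on intervals and visualizations, and a competent analyst might mark arms on the plots anyway. Whether markers move together across all treated participants is also a legitimate descriptive question, different from the within-arm one. All of this stands, and it keeps the point small. It does not close the gap: the plan does not say which question is asked, and the plain coefficient is what the line literally yields.

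A reader might infer more than the documents support:

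- *That the SAP prescribes a single pooled coefficient.* It does not use either term; arm handling is simply absent.
- *That markers differing between arms will look linked.* They can. Both must shift, and by a good deal; even at 2.45 SD in both, fewer than half of simulated trials reach nominal significance.
- *That the trial expects 2.45 SD in both markers.* That figure is for exosome proteins. For blood and CSF markers protocol section 10.2 hypothesises a difference without a size.
- *That the analysis will be used to argue that exosome changes reflect AD pathology.* Neither document says so. The supportable consequence is the general Phase 2 use in protocol section 2.3.3.
- *That the issue is association within persons.* With one Screening-to-Week 8 change in CSF or plasma per participant, any such correlation is between participants. Adjustment makes it within-arm, no more.
- *That fewer CSF samples make false significance more likely.* They make it less likely, as step 4 shows.

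**Conclusion.** The concern holds in a limited form. SAP section 9.1 does not account for arm, and a plain Spearman coefficient over both arms would mix within-arm association with between-arm differences. How much depends on the CSF or plasma shift, for which the documents give no value. Across the assumed range, the mean spurious coefficient runs from 0 (only one marker shifts), through 0.15 (1 SD in both) and 0.27 (2.45 and 1 SD), to 0.47 (2.45 SD in both). These figures assume normal markers, equal within-arm SDs, zero within-arm correlation and 12 + 4 complete pairs. The primary analysis is untouched. This is a worthwhile but minor correction to an exploratory analysis.

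**What to change.** Replace the correlation line in SAP section 9.1 with:

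> Spearman correlations between Week 8 changes in CSF/plasma markers and Week 8 changes in exosome biomarkers, adjusted for treatment arm (partial Spearman), with 95% CI; scatterplots coded by arm. Any pooled unadjusted coefficient will be labelled as not separating within-arm association from between-arm differences.

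This also settles which exosome variable and visit are used. It needs no new data and costs one degree of freedom. Estimates will remain imprecise, above all in the voluntary CSF subset, and the analysis should stay labelled exploratory and descriptive.

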9.2 Cognitive Outcomes

- FLAME domain scores: change from baseline
- MoCA: baseline vs Week 8
- Individual-level change plots

No adjustment for practice effects due to short follow-up.

10 Interim Analyses

No formal interim efficacy analyses are planned. Safety data will be reviewed on an ongoing basis by the medical monitor and DSMB according to protocol.

11 Changes from Protocol

Any deviations from protocol-specified analyses will be documented and justified in the Clinical Study Report (CSR).

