Neuropsychology assessments will be conducted using the FLAME computer-based domain composites for memory, executive function, attention and sustained attention to evaluate changes over the 8-week treatment period in the phenserine treated participants compared to those who received donepezil. In addition, evaluate overall cognitive changes using the Montreal Cognitive Assessment (MoCA).

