To evaluate disease modification by assessing changes in specific biomarkers of Alzheimer's Disease (AD) in cerebrospinal fluid (CSF): A β 1-40, A β 1-42, Tau, and p-tau, and in blood plasma: p-tau217 and Nfl.	Assess changes in Alzheimer's Disease (AD) biomarkers in cerebrospinal fluid (CSF): A β 1-40, A β 1-42, Tau, and p-tau, and in blood plasma: p-tau217 and Nfl.
To assess phenserine's potential short-term effects on specific cognitive tasks using the FLAME Memory Composite and other cognitive sub-tests	Neuropsychology assessments will be conducted using the FLAME computer-based domain composites for memory, executive function, attention and sustained attention to evaluate changes over the 8-week treatment period in the phenserine treated participants compared to those who received donepezil.
To assess effect on global cognition	The Montreal Cognitive Assessment (MoCA) will be administered at baseline and at the end of the study to evaluate changes in overall cognitive function across multiple domains, including visuospatial abilities, language, attention, memory, and executive function.

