3.2.3. Exploratory Outcome Measures

Neuropsychology assessments will be conducted using the FLAME computer-based domain composites for memory, executive function, attention and sustained attention to evaluate changes over the 8-week treatment period in the phenserine-treated participants compared to those who received donepezil. The results of these assessments will be compared to changes observed on exosome biomarkers to identify similar trends across the treatment arms and in individual participants.

In addition, the Montreal Cognitive Assessment (MoCA) (24) will be used at baseline and end-of-treatment to assess for any changes in cognition over the course of the treatment period.

CSF or blood AD or Tau markers or amyloid PET will be analyzed for typical AD features as an inclusion criterion (see Section 5). Blood will also be collected at the Week 8 visit to evaluate any changes in blood-based biomarkers across the two groups. Among consenting participants, CSF will also be collected and stored for evaluation of CSF-specific biomarker changes. All procedures will be performed according to highly standardized procedures in accordance with the defined biobanking pre-analytical standard operating procedures (SOPs) of the BIOMARKAPD project (25).

4. Study Design

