10.2. Statistical Hypotheses

- **Primary Hypothesis:**

- There is a difference between phenserine and donepezil in terms of their effect on the primary endpoint, which involves changes in exosome biomarkers of pre-programmed cell death, synaptic integrity and function, neuroinflammation, and AD-related protein trafficking.

- **Secondary Hypothesis**

- Phenserine and donepezil do not differ in their safety and tolerability profiles, as measured by the rate and severity of adverse events (AEs).

- **Exploratory Hypothesis:**

- Phenserine has a different effect compared to donepezil on short-term cognitive performance, as measured by the FLAME Memory Composite and other cognitive sub-tests.
- Phenserine and donepezil differ in their effects on changes in blood and cerebrospinal fluid (CSF) biomarkers, including A β 1-40, A β 1-42, Tau, p-tau, p-tau217, and NfL

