2.3 Exploratory Objectives

- Changes in CSF and plasma AD biomarkers
- Short-term cognitive effects using FLAME and MoCA

Endpoints are defined exactly as per Protocol Section 3 and Table 2

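### SAP 9.2 gives no phenserine-minus-donepezil estimate for cognition, and short follow-up is not a sound reason to set practice effects aside

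*SAP*

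**What the plan says.** SAP 9.2 has three analysis items: "FLAME domain scores: change from baseline", "MoCA: baseline vs Week 8", and plots of individual change. One sentence follows: "No adjustment for practice effects due to short follow-up".

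The protocol asks a comparative question of FLAME. The exploratory hypothesis in Protocol 10.2 reads: "Phenserine has a different effect compared to donepezil on short-term cognitive performance, as measured by the FLAME Memory Composite and other cognitive sub-tests". The FLAME endpoint in Protocol Table 2 concerns "changes over the 8-week treatment period in the phenserine treated participants compared to those who received donepezil". SAP 2.3 brings these definitions in: "Endpoints are defined exactly as per Protocol Section 3 and Table 2".

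MoCA is different. Protocol 3.2.3 uses it "to assess for any changes in cognition over the course of the treatment period", with no comparator, and the hypothesis in Protocol 10.2 does not name it.

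Protocol 10.3 does not close the gap. For exploratory outcomes it provides only descriptive statistics of change from baseline at the final assessment. The SAP writes out a method for comparing the arms in section 7.2 only, for the exosome biomarkers.

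**The concern.** The plan holds a comparative FLAME endpoint for which no comparative analysis is specified. An analyst who follows SAP 9.2 literally will report mean change, perhaps by arm, and stop there. That quantity is drug effect plus practice gain plus anything else that moves scores over eight weeks, and no single arm can separate them.

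The reason given for ignoring practice does not help. FLAME and MoCA are each given at baseline and again at Week 8, and neither document mentions alternate forms or a familiarisation session. A short interval leaves little time for familiarity with the tests to fade.

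What is at stake is interpretation. SAP 2.3.2 asks for a 95% interval with every efficacy estimate, so a within-arm change could appear with an interval that excludes zero and be taken for a short-term cognitive effect. Protocol 2.3.3 says that the assessments together, cognition among them, will guide the choice of doses and outcome measures for Phase 2.

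**Working it through.** **The plan's own figure.** There is none for cognition. The only sample-size figure, 4 per arm for a 2.45 SD difference, concerns the exosome outcome (Protocol 10.3). It reproduces (82.1% power by the noncentral t) but has no bearing here.

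**Inputs from the documents.** 12 phenserine and 4 donepezil participants (SAP 3); cognitive tests at baseline and Week 8 in both arms (Protocol Table 1); two-sided 95% intervals (SAP 2.3.2).

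**Inputs assumed.** Practice gain g of 0.2, 0.3 or 0.5 score SD, equal in both arms; retest correlation r of 0.6 to 0.8; equal score SD at both visits; normal scores; no drug effect. None of these is in the documents.

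**Step 1: what each quantity estimates.**
- Phenserine change = phenserine effect + g.
- Donepezil change = donepezil effect + g.
- Difference = phenserine effect − donepezil effect. The gain cancels in expectation because allocation is random and the schedule is common.

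**Step 2: how often the phenserine interval would exclude zero from practice alone.** The SD of change is √(2(1 − r)) score SD: 0.894, 0.775 and 0.632 at r = 0.6, 0.7 and 0.8. The standardised gain is g divided by that SD. The chance that a one-sample 95% interval with n = 12 excludes zero follows from the noncentral t with 11 df and noncentrality √12 × g/SD.

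| Gain (score SD) | r = 0.6 | r = 0.7 | r = 0.8 |
|---|---|---|---|
| 0.2 | 11% | 13% | 17% |
| 0.3 | 19% | 23% | 32% |
| 0.5 | 42% | 53% | 70% |

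With no gain the figure is 5%. If the gain is instead expressed in SDs of the change score, 0.2, 0.3 and 0.5 give 9.7%, 15.8% and 35.3%. The scale matters: at r = 0.7, 0.2 score SD is 0.2/0.775 = 0.26 change SD.

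**Step 3: the same situation with the arms contrasted.** With a common gain of 0.3 or 0.5 change SD and no drug effect, 100,000 simulated trials of 12 against 4 gave a mean difference of about zero, and the interval excluded zero in 5.0% and 5.1%.

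**Step 4: what the contrast costs in precision.**
- Difference in change, unadjusted: 2.145 × √(1/12 + 1/4) = 2.145 × 0.577 = 1.24 SD of change. At r = 0.7 this is 1.24 × 0.775 = 0.96 score SD.
- Adjusted for baseline, r = 0.7: 2.160 × √(1 − 0.49) × 0.577 = 0.89 score SD, ignoring the small extra term for chance baseline imbalance.
- Within phenserine alone: 2.201/√12 = 0.64 SD of change. This is narrower, but around a quantity that contains the gain.

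For scale, Protocol 2.3.1 quotes symptomatic effects of 0.3 to 0.4. If those units are read as SDs of change, power for 12 against 4 is 7.7% at 0.3 and 9.9% at 0.4, and 80% power needs about 1.74.

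**The case against.** Several counterarguments have force.

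- **A replaced hypothesis.** A reader might infer that the SAP has exchanged the comparison with donepezil for a test of no change over time. The documents do not support that. SAP 9.2 states no null, test or decision rule, and SAP 2.3 imports the comparative FLAME endpoint. What can be shown is an omitted estimate.
- **Inflated Type I error.** The percentages above could be read as error rates of the plan. They are not. SAP 2.3.2 makes p-values descriptive and does not treat the intervals as formal inference, and SAP 5 excludes formal hypothesis testing. They show only how often a reader could be misled, under inputs that the documents do not supply. With no practice gain there is no excess.
- **MoCA as a second mismatch.** The protocol itself frames MoCA as change over the treatment period, so SAP 9.2 agrees with it there. Practice still affects how the MoCA change can be read.
- **The SAP follows the protocol.** SAP 9.2 is consistent with Protocol 10.3. The tension is partly inside the protocol, between 10.3 and 10.2.
- **A practice adjustment is needed.** It is not, once the arms are contrasted. Declining to adjust is acceptable; the reason given for it is what fails.
- **Little is gained.** Cognition is exploratory, and an interval of about ±0.9 score SD will not resolve effects of 0.3 to 0.4. True, but the wide interval shows what 12 against 4 can support on the question asked.

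What remains is the missing FLAME contrast and the unsound reason.

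**Conclusion.** The concern holds in a limited form. SAP 9.2 leaves the between-arm FLAME question of Protocol 10.2 and Table 2 without an estimate, and Protocol 10.3 has the same gap. The within-arm summaries that it does specify carry the full practice gain.

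That the gain cancels rests on randomisation and the common test schedule, and assumes practice is equal in the two arms. The size of any misreading cannot be settled from the documents. The range of about 11% to 70% rests wholly on the assumed gains and correlations and is illustration only. The consequence is possible misinterpretation of an exploratory outcome, not a false confirmatory claim. The point should be corrected because the remedy is cheap and the results feed into Phase 2 planning.

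**What to change.** In SAP 9.2:

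1. Make the main cognitive estimate the phenserine-minus-donepezil difference at Week 8 for each FLAME composite, adjusted for the baseline score, with a 95% interval.
2. Report the same estimate for MoCA as supporting information.
3. Keep the within-arm changes and individual plots, labelled *includes practice effect; not an estimate of drug effect*.
4. Replace the sentence on short follow-up with: *practice effects are assumed common to both arms and cancel only in the between-arm difference*.

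The cost is SAP wording and one model per score, on data already collected. The drawback is the imprecision shown above, so the result should stay descriptive, and the SAP should say so beside the estimate. A simple difference in mean change would also cancel a common gain, with a somewhat wider interval.
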